## Research Protocol/Protocol Addendum Template

---

### **Title**

Reengaging rural patients in VA mental health care after VA-community care network referral.

### **Specific Aims/Purpose**

Rural patients who receive mental health treatment through VA-Community Care Networks (VA-CCN) represent a special population of high-risk patients because they have demonstrated an acute mental health need yet are not routinely included in VA suicide prevention programming. This is a critical gap in care. We have previously developed a suicide prevention intervention to decrease suicide risk in patients during high-risk transition scenarios. The intervention is called the VA Brief Intervention and Contact Program (VA BIC) and is an adaptation of the successful World Health Organization Brief Intervention and Contact Program (WHO BIC). VA BIC aims to prevent suicide by educating VA patients around suicide risk, promoting treatment engagement, and increasing social connectedness. Our pilot work with VA BIC in VA inpatient and outpatient settings suggests that VA BIC may decrease suicidal ideation, reduce hopelessness, increase social connectedness, and improve treatment engagement. A quality improvement project of BIC at six rural VA facilities also found that on average, patients rate BIC as excellent and site staff perceive that BIC is implementable.

Building off our pilot work with VA BIC, we propose a two-year project arc to address current gaps in care by adapting the VA BIC intervention to promote re-engagement in VA care for VA-CCN patients and prevent suicide. Our project will consist of three phases. **In Phase 1**, we will develop a reliable method to incorporate our VA BIC intervention into care processes for rural patients who are discharged from VA-CCN mental health treatment settings. This adaptation will extend VA BIC to the VA-CCN. Our adaptation will be called the Building VA Engagement, Self-efficacy, and Social Support To Prevent Suicide (BESST) intervention. During Phase 2, we will pilot test the BESST intervention in a cohort of patients. Finally, during Phase 3, we will conduct a randomized trial of BESST versus usual care to determine whether BESST improves re-engagement in VA-provided mental health services and suicide-related outcomes in the VA-CCN population

### **Study Objectives and Specific Aims**

The overall goal of our proposed work is to develop a key resource for rural VA facilities to use to keep patients who are referred to (and discharged from) VA-CCN mental health treatment settings involved in VA care and to prevent suicide. To achieve our overall goal, we intend to pursue the following aims:

**Aim 1:** During phase 1, we will determine a reliable method to incorporate our VA BIC suicide prevention intervention into care processes for rural patients discharged from VA-CCN mental health treatment settings.

## Research Protocol/Protocol Addendum Template

**Hypothesis:** We will develop a reliable method to incorporate VA BIC into care processes for rural patients discharged from VA-CCN mental health treatment settings. The adaptation will be called the Building VA Engagement, Self-efficacy, and Social Support To Prevent Suicide (BESST) intervention.

**Aim 2:** During phase 2, we will pilot test the BESST intervention in four to six rural patients who are referred to (and discharged from) a VA-CCN mental health treatment setting.

**Hypothesis:** We will obtain data on the feasibility of studying the BESST intervention in rural patients who are referred to (and discharged from) a VA-CCN mental health treatment setting. We will identify any further modifications that may be required prior to studying BESST in this population.

**Aim 3:** During phase 3, we will conduct a randomized trial of the BESST intervention versus usual care in rural patients who are referred to (and discharged from) VA-CCN mental health treatment settings. We aim to determine whether the BESST intervention can improve suicide-related outcomes in this population.

**Hypothesis:** We will determine whether the BESST intervention reduces suicidal ideation and hopelessness and improves social connectedness and treatment engagement in rural patients who are referred to (and discharged from) VA-CCN mental health treatment settings.

**Note:** As shown in **Table 1**, we will develop a reliable method to incorporate our VA BIC intervention into care processes for rural patients who are discharged from VA-CCN mental health treatment settings.

**Table 1:** Proposed phases of study of the BESST intervention in rural patients.

Phase	Aim	Proposed study activities during phase of work
Phase One	Aim 1	

• Recruit three rural VA facilities and their affiliated VA-CCN sites.

• Use an interview guide to interview site staff about current VA-CCN processes of care and to determine a reliable method to incorporate VA BIC into these processes. The adaptation will be called BESST.

Phase Two	Aim 2	

• Pilot study of BESST in 4 – 6 patients who access VA-CCN care.

• Finalize the BESST manual.

Phase Three	Aim 3	

• Use results of Phase 1 and 2 to inform the design of a pilot, randomized trial of the BESST intervention for VA-CCN mental health settings.

BESST = Building VA Engagement, Self-efficacy, and Social Support To Prevent Suicide; VA BIC = VA Brief Intervention and Contact Program; VA-CCN = VA Community Care Networks;

### **Scientific Rationale and Significance**

A growing number of rural patients receive portions of their care in VA Community Care Network (VA-CCN) settings. In fact, VA researchers have observed that nearly 40% of recipients of VA-CCN services live in rural areas. In Fiscal Year (FY) 2021, the

## Research Protocol/Protocol Addendum Template

---

White River Junction VA Medical Center (WRJ VAMC) reported over 300 VA-CCN inpatient and residential mental health stays among its patient panel. Growth in VA-CCN use is concerning because **rural patients may experience worse outcomes in VA-CCN settings due to problems such as breakdowns in communication.** Importantly, this may prompt patients to disengage from VA-delivered care following a VA-CCN stay.

Rural patients are at the highest risk for suicide following an inpatient or residential mental health stay for the treatment of mental health conditions or substance use disorders (SUD). Several factors may contribute to this finding such as poor social support, limited engagement in care and poor access to care. The VA has developed a suite of strategies to address suicide risk in patients following a mental health discharge. The **VA suicide prevention program, however, does not extend to patients who are treated in VA-CCN mental health treatment settings.** In fact, there is no evidence-based approach to assist rural patients with re-engaging with VA care after a VA-CCN discharge and to mitigate their suicide risk. These findings highlight a crucial gap in the VA's efforts to keep rural patients engaged in VA care and to prevent suicide.

We developed a suicide prevention strategy called the VA Brief Intervention and Contact Program (VA BIC). A key goal of VA BIC is to mitigate suicide risk by helping rural patients to stay engaged in VA care after mental health discharge from a VA treatment program. Our pilot work and testing of VA BIC at the White River Junction VA Medical Center suggests that VA BIC may reduce suicidal ideation and hopelessness and improve social connectedness and treatment engagement. Based on our positive results, **we believe that VA BIC can be adapted to meet the needs of rural patients who are referred to (and discharged from) VA-CCN mental health settings.** Our VA BIC adaptation will be called the Building VA Engagement, Self-efficacy, and Social Support To Prevent Suicide (BESST) intervention. The BESST intervention will aim to increase engagement in VA care among rural patients and to decrease their suicide risk. Ultimately, our work will lead to the development of a key resource for rural VA facilities to use to keep patients who are referred to (and discharged from) VA-CCN mental health settings involved in VA care and to prevent death by suicide.

### **Preliminary Studies**

Several brief interventions have been developed to address the risk for suicide following psychiatric and emergency room discharge. In a meta-analysis of randomized controlled trials (RCTs) of suicide prevention strategies, Riblet et al. (2017) identified a single intervention, the World Health Organization Brief Intervention and Contact (WHO BIC) Program, that is proven to prevent suicide following psychiatric discharge. The WHO BIC (1) facilitates patient engagement through educating patients about suicide risk and (2) provides patients with regularly-scheduled professional support after discharge by helping patients adhere to their discharge care plan through in-person and telephone contact. The WHO BIC also aims to ensure continuity of care after discharge by facilitating the communication of emergent patient

## Research Protocol/Protocol Addendum Template

---

needs and concerns to their outpatient providers. Yet, the WHO BIC has not been studied in high-income countries or in U.S. veterans. Our pilot work demonstrated that the WHO BIC may address systematic vulnerabilities in the discharge process and align with hospitalized veterans' preferences for treatment.

We conducted a pre-post study of an adapted version of WHO BIC (called VA *BIC*) in nine psychiatrically hospitalized Veterans at the White River Junction VA Medical Center (WRJ VAMC). We found that rural Veterans exposed to VA BIC experienced significant and clinically meaningful improvements in suicidal ideation at one and three months after discharge. We also observed significant improvements in related measures of suicide risk including hopelessness and connectedness. Patients had high treatment engagement after discharge. Subsequently, we performed a pilot RCT of VA BIC in 19 psychiatrically hospitalized Veterans. Aligned with the results of our pre-post study, we found that VA BIC had a medium or large effect on suicidal ideation, hopelessness, social connectedness at one month after discharge. Furthermore, the effect on social connectedness remained large at three months. VA BIC also had a medium effect on treatment engagement.

The study of VA BIC during other high-risk transition scenario settings has also yielded promising results. We performed a pilot RCT of VA BIC in 19 Veterans who presented to a primary care mental health walk-in clinic for a new mental health intake appointment and were at risk for suicide. We identified that it was feasible to conduct a virtual trial of the intervention in this population. Moreover, the results suggested that Veterans assigned to the intervention may experience improvements in suicidal ideation as well as higher treatment engagement. We are also currently completing a study of the VA BIC in Veterans who are admitted to a VA residential treatment program for the management of substance use disorder. We were able to meet our recruitment goal of 20 Veterans. The results of this study are not yet available. Finally, we collaborated with the VA Office of Rural Health, the VA National Center for Patient Safety, and the VA Office of Systems Redesign in a quality improvement (QI) project that examined the BIC program in six, rural VA facilities. The results of the QI work suggested that Veterans on average rate the BIC program as excellent and VA providers perceive that BIC is implementable.

To the best of our knowledge there have been no studies of targeted interventions for rural patients that address suicide risk and treatment engagement after discharge from VA-CCN mental health treatment settings. The VA BIC (or any related adaptations) have also not been tested in these settings. Therefore, as a next step, we propose to determine current processes of care for rural patients who are referred to (and discharged from) VA-CCN mental health treatment settings. We will then develop, and pilot test a VA BIC adaptation (called the BESST intervention) that is optimized to meet the needs of rural patients who are referred to (and discharged from) VA-CCN mental health treatment settings.

## Research Protocol/Protocol Addendum Template

---

Finally, we will conduct a randomized trial of the BESST intervention versus usual care in rural patients who are referred to (and discharged from) VA-CCN mental health treatment settings. The results of our work will ultimately lead to the development of a key resource for rural VA facilities to use to keep patients who are referred to (and discharged from) VA-CCN mental health treatment settings involved in VA care and to prevent death by suicide.

**Note we report here only on the portion of the protocol that relates to the pilot RCT that is registered at clinicaltrials.gov at the number listed on the first page. Thus, pages 6-12 are intentionally excluded from the document as they pertain only to aims 1 and 2 of the larger project.**

### **Project Proposal, Phase 3, Aim 3**

To test our hypotheses as described above, we propose to conduct an assessor - blinded RCT comparing the BESST intervention plus standard care to standard care alone. We will enroll up to 25 patients who are 18 years or older and are being discharged from a VA-CCN mental health treatment setting. The primary aim is to determine whether the BESST intervention reduces suicidal ideation at one and three months after discharge. The secondary aim is to evaluate the impact of the BESST intervention on other related measures of suicide risk including hopelessness, social connectedness, fatal/non-fatal suicide attempts and treatment engagement.

**Randomization:** Prior to the start of study enrollment, the study team otherwise not involved in recruitment will independently prepare allocation cards using a permuted block schedule. The same study staff member will then put these prepared allocation cards into sealed, opaque, numbered envelopes. After obtaining consent and completing the baseline assessment (see description below), the study staff member will take the next numbered envelope from the box (described above) and open the envelope to determine the patient's assignment. In the event that the patient has been assigned to the intervention, the study staff will notify the intervention staff in order that the intervention staff can initiate the intervention. Otherwise, the patient will be informed that they have been assigned to usual care.

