**Baseline Characteristics:** We will collect socio-demographic data from the electronic medical record such as age, sex, marital status and service history (e.g., branch, era, combat exposure). We will also collect diagnostic information using either the MINI International Neuropsychiatric Interview (MINI), which has been validated against the Structured Clinical Interview for Diagnostic and Statistical Manual of Mental Disorders (DSM). The MINI is a short, structured diagnostic interview that, on average, takes about 15 minutes to administer. We will ask about any history of suicide attempts using the validated Columbia Suicide Severity Rating-Scale (C-SSRS). The C-SSRS includes a seven-item subscale that assesses for actual and interrupted suicide attempts.

**Primary Outcome (Suicidal Ideation):** The primary outcome will be assessed using the Beck Scale for Suicidal Ideation (BSS) (Specific Aim 1). Patients will be asked about their current suicidal ideation (i.e., past week) at baseline and at the one-month and three-month follow-up

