## Research Protocol/Protocol Addendum Template

---

secondary aims of interest of this study. We will assess for statistically significant differences in baseline study characteristics such as age, sex, race, and mental health diagnosis, between study arms using *t*-tests for continuous measures and chi-squared tests for dichotomous variables. We will report these results using 95% confidence intervals (CI) and *P*-values. We will define statistical significance as a *P*-value < 0.05.

**Specific Aim 1:** We will generate descriptive summary statistics (e.g., means and standard errors, medians) and graphical displays for the BSS total scores at baseline and at each of the follow-up assessments. In the case of the pilot study of the BESST intervention in up to six patients, we will use a repeated measures analysis of variance (ANOVA) test to assess for changes in continuous variables in the first three months after discharge. Second, if the repeated measures ANOVA suggested a significant difference in means across time, we will perform a post-hoc, pair-wise comparison of means at baseline and at each follow-up using a two-sample *t*-test.

With regards to the RCT of the BESST intervention, we will use a generalized linear mixed model to assess for changes in continuous variables in the first three months after discharge. We will consider allocation of study arm (categorical measure) and time (continuous measure) as fixed effects. Random effect will be used to account for correlation that arises from repeated measures of the same individual. We will assume a linear effect and model changes in suicidal ideation over time. We will calculate 95% CI and *P*-values and will define a *P*-value of < 0.05 to be statistically significant. We will use the maximum likelihood ratio to account for any missing data. Based on available evidence, we hypothesize that the BESST intervention plus standard care will lead to a significant reduction in suicidal ideation after discharge.

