**Specific Aim 2:** We will generate descriptive summary statistics (e.g., means and standard errors, medians) and graphical displays for our secondary outcomes of interest at baseline and at each of the follow-up assessments. In the case of the pilot study of the BESST intervention in up to six patients, we will use a repeated measures analysis of variance (ANOVA) test to assess for changes in continuous variables in the first three months after discharge. Second, if the repeated measures ANOVA suggested a significant difference in means across time, we will perform a post-hoc, pair-wise comparison of means at baseline and at each follow-up using a two-sample *t*-test.

With regards to the RCT of the BESST intervention, we will use a generalized linear mixed model to assess for changes in continuous variables in the first three months after discharge. We will calculate the associated 95% confidence intervals and *P*-values. As with the BSS, we will consider allocation of study arm (categorical measure) and time (continuous measure) as fixed effects. Random effect will be used to account for correlation that arises from repeated measures of the same individual. We will assume a linear effect and model changes in suicidal ideation over time. We will define a *P*-value of < 0.05 to be statistically significant. We will use the maximum likelihood ratio to account for any missing data. Based on available evidence, we hypothesize that the BESST intervention plus standard care will lead to a significant reduction in our secondary outcomes after discharge.

For the categorical measure of healthcare utilization, we will use chi-squared tests to compare findings between study arms.

**Specific Aim 3:** We will not be powered to detect a statistically significant difference between study arms with regards to suicide deaths and suicide attempts. These events are very difficult to examine in a clinical trial. A study would need to recruit well over 1,000 patients. Because we assume that few events will be observed in either arm, we plan to summarize our results by

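### The plan does not name the BSS comparison that decides the primary aim, and its secondary scales are judged at an unadjusted P < 0.05 with no testing order or exploratory label

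*Combined protocol and SAP*

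**What the plan says.** The primary aim, in Project Proposal, Phase 3, Aim 3, covers two follow-up times: "The primary aim is to determine whether the BESST intervention reduces suicidal ideation at one and three months after discharge". Neither month is marked as decisive, and the text does not say whether one or both must show a benefit. The outcome itself is single: the BSS total score.

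Under Statistical Analyses, Specific Aim 1, the randomized comparison is one mixed model. Its terms are given as "We will consider allocation of study arm (categorical measure) and time (continuous measure) as fixed effects", with a random effect for repeated measures. The time effect is described by "We will assume a linear effect and model changes in suicidal ideation over time". No arm-by-time term is listed and no contrast is named. The decision rule is that the team "will define a *P*-value of < 0.05 to be statistically significant".

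Specific Aim 2 of the same section repeats the model for continuous secondary outcomes and repeats the threshold: "We will define a *P*-value of < 0.05 to be statistically significant". It adds chi-squared tests for categorical healthcare utilization, without restating a threshold, and hypothesizes a significant reduction in the secondary outcomes. The project-level Aim 3 hypothesis is that BESST "reduces suicidal ideation and hopelessness and improves social connectedness and treatment engagement".

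No testing order, adjustment or exploratory label is given for these outcomes. Suicide attempts and deaths are treated differently: Specific Aim 3 of the analysis section makes them descriptive only.

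**The concern.** There are two gaps.

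First, the aim and the model do not meet. The aim asks about arm differences at one and three months, but the model as listed has one arm term spanning all three assessments, including baseline. Someone must later choose between that coefficient, a slope difference, a month-specific difference or an average. If the choice is made with data in hand, the 0.05 attached to the primary result loses its meaning.

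Second, the secondary claims have no lead measure. Connectedness has two scales (INQ-15 and MSPSS). Engagement has the coping scale (SRCS), general self-efficacy (GSE) and several utilization measures. A statement that BESST improves connectedness or engagement could rest on whichever measure happens to cross 0.05.

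This matters because parts of the protocol read as confirmatory. Sample Size says that up to 25 patients give sufficient power for a significant improvement, and Benefits says the work will address effectiveness more definitively.

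**Working it through.** **Plan's own figure.** The only error rate in the documents is the per-test 0.05. It is set, not derived, so there is nothing to reproduce beyond one test at 5%. Sidedness is not stated; I assume two-sided tests.

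**What the literal model estimates.** Let d0, d1 and d3 be the true arm differences in BSS at baseline, one month and three months. With arm and time as the only fixed effects, a random intercept and complete data, the arm coefficient estimates

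(d0 + d1 + d3) / 3.

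Baseline is assessed before the allocation envelope is opened, so d0 = 0 in expectation and the coefficient targets (d1 + d3) / 3. If the difference is the same, d, at both months, the coefficient targets 2d/3. A 5-point difference (the size that Sample Size calls clinically meaningful) would appear as 5 × 2/3 = 3.3 points. The test still holds 5% under no effect, but it estimates neither month's difference nor their average.

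**If an arm-by-linear-time term were added.** With slope difference b, the arm differences in change from baseline at months 1 and 3 are b and 3b. Their Z statistics are identical, so this is one test at 5%, not two.

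**If the two months were tested separately and either counted.** For independent tests the error is 1 − 0.95² = 9.75%. For correlation ρ between visits (assumed; the documents give none), the bivariate normal gives 9.1% at 0.5 and 7.8% at 0.8. If both months were required, there would be no inflation.

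**Counting the secondaries.** Outcome Measures lists six scales: BHS, INQ-15, MSPSS, SRCS, GSE and TLFB. I count one test each and leave out the two SRCS subscales. Utilization adds amount of contact, time to first appointment, and disruptions of care counted as one measure or as two (no-shows, cancellations). That makes 6 + 3 = 9 or 6 + 4 = 10. Attempts and deaths count as zero, and baseline comparisons are not efficacy tests.

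**Chance of at least one P < 0.05 when every null is true.** Independent tests: 1 − 0.95^k. For a common correlation ρ, take Z_j = √ρ·U + √(1 − ρ)·E_j with U and E_j standard normal, and compute P(any |Z_j| > 1.96).

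| k | ρ = 0 | 0.3 | 0.5 | 0.7 | 0.9 |
|---|---|---|---|---|---|
| 6 scales | 26.5% | 24.1% | 20.7% | 16.4% | 10.8% |
| 9 measures | 37.0% | 32.6% | 26.9% | 20.2% | 12.4% |
| 10 measures | 40.1% | 35.1% | 28.7% | 21.3% | 12.8% |

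The correlations are assumptions. Every value tried leaves the chance above 5%.

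**The case against.** The strongest reply is that the plan is less loose than it looks. It names one primary outcome, one model and one threshold. Pairwise comparisons between visits belong to the six-patient phase 2 pilot, not to the randomized trial. Outcomes are ranked primary and secondary, 95% confidence intervals are planned, and the trial is called a pilot.

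Most of this stands, and it rules out several stronger readings that a reader might infer:

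- *That two primary tests at 0.05 are planned.* They are not. One linear-time model is specified, and the aim's wording joins the two months with *and*, which could mean both are needed. The 8 to 10% figure is conditional on an analysis that the plan leaves open but does not prescribe.
- *That requiring both months would cost a known amount of power.* The documents give no power value from which to compute it.
- *That a stated 5% overall error is breached.* The 0.05 is per test, and no family-wise rate is claimed.
- *That ten or more secondaries share the same explicit threshold.* The Specific Aim 2 threshold sits with the mixed model for continuous outcomes. The chi-squared sentence states none, and no method is named for time to first appointment. Nine to ten is the upper count.
- *That an isolated significant secondary is probably chance.* The table gives the probability of any false positive when all nulls are true, not the probability that an observed finding is false.

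The reply does not close the two gaps. A single arm coefficient that includes baseline is not an effect at one and three months. The pilot label also sits beside claims of sufficient power and hypotheses of significant benefit. The plan restricts attempts and deaths to description but does nothing comparable for the other secondaries.

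**Conclusion.** The point holds in this form: the contrast that decides the primary aim is not named, and the secondary scales carry unadjusted significance statements without an order or label.

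The first gap does not rest on any assumed correlation. It follows from setting the aim beside the listed model terms; only the factor of two-thirds assumes complete data, a random intercept and equal effects at both months. Any inflation of the primary error is limited to about 8 to 10%, and arises only if the months are tested separately and either counts. For the secondaries, the chance of at least one false significant result is about 21 to 27% for six scales and 27 to 40% for nine to ten measures at common correlations of 0.5 down to 0, falling to about 11 to 13% at 0.9. These figures assume two-sided normal tests with all nulls true.

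This concerns how single results should be interpreted and should be settled before analysis. It does not show that the trial's stated error rate is wrong.

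**What to change.** In Project Proposal, Phase 3, Aim 3 and in Statistical Analyses, Specific Aim 1, name one primary BSS contrast, tested once at 0.05. Either the arm difference averaged over the one- and three-month visits or the arm difference at one named month would serve. Set the model terms so that this contrast can be estimated; arm plus linear time alone cannot isolate it. Report each month's estimate with a 95% confidence interval and no separate significance claim.

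In Specific Aim 2, replace the significance threshold with estimates and 95% confidence intervals, labelled exploratory and unadjusted for multiplicity, and reword the hypothesis of a significant reduction to match.

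The cost is a small change to the model specification and some wording, with no extra patients or data. The sponsor gives up claiming significance on a single month outside the named contrast, or on a single secondary measure.
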